PROTOCOL OUTLINE AND GUIDELINES

Investigators must submit well-organized, detailed information about the study, demonstrating sound research design that minimizes risks to the subject. PI should assure that the content outlined below is addressed and may exercise some discretion as to how the information is organized. The quality and content of the protocol should demonstrate that scientific and merit review of the study has occurred at the departmental level prior to submission to the IRB.

1. PROTOCOL INFORMATION

Title: Low-Titer Type O Positive Whole Blood Versus Component Therapy for Emergent Transfusion in Trauma Patients

Funding Source: Internal

Phase of Study: RCT (Phase IV)

Version Date of Protocol: 3/25/2021

4. STUDY INFORMATION

Location(s) of Research Activity: Loma Linda University Medical Center

Expected Start/Stop Dates of Research: 07/01/2021 to 06/30/2023

Special Time Sensitivities: N/A

Type of Research: Randomized controlled trial of two alternative standard-of-care transfusion strategies

5. INCLUSION / EXCLUSION CRITERIA

Criteria for inclusion of subjects: Adult male patients brought to the emergency department as Level A trauma activations who are receiving emergency blood transfusion

Criteria for exclusion of subjects (other than those opposite the inclusion criteria): Female patients (specifically excluded due to risk of alloimmunization of Rh-negative female patients of childbearing age against Rh-positive blood), children, prisoners, patients classified as dead on arrival who will still be randomized but who will have their data excluded to eliminate the effect of survivor bias in the remaining subjects.

6. SUBJECT RECRUITMENT & SCREENING

Based on the results from Cotton et al, median transfusion in the component therapy group was 6 PRBC in the first 24 hours and 4 PRBC equivalents in the whole blood group. The standard deviation (estimated from the interquartile range) was approximately 4. Thus with an expectation of alpha = 0.05 and expected power of 90% to detect a similar 2 unit difference in transfusion volume, a sample size of 190 should be sufficient; thus our projected sample size of 200 should be more than adequate. Age range will be 18 years and older, and only males will be included in the study. Our expected racial/ethnic distribution will be approximately 60% white, 15% black, 8% Asian, and 18% other race. No actual recruitment will be performed; rather all qualifying patients will be included. Consent waiver is being requested.

7. INFORMED CONSENT PROCESS

Consent waiver is being requested.

8. STUDY DESIGN

a. Background or rationale for this study.

Whole blood transfusion was used in World War I, World War II, Korea and Vietnam. By the end of the Vietnam conflict, whole blood had been separated into components for ease of use and more focused transfusion. As a result, transfusion practices did not catch up with the available units. More recent investigations have revealed that patients have fewer deaths from hemorrhage when the ratios of FFP:RBC units and platelet:RBC units approaches 1:1. Furthermore, the success of “walking blood banks” with fresh whole blood transfusion in the 2nd Iraq war and the war in Afghanistan have prompted new interest in the civilian use of whole blood. While civilian centers cannot use walking blood banks as we do not have a pre-screened population from which to draw, low-titer type O positive whole blood (LTOWB) can be used. One LTOWB unit is equivalent to one unit of PRBC and one unit of FFP. While LTOWB has been studied, the inclusion criteria for past studies has been less inclusive than in this trial, specifically excluding patients with severe traumatic brain injuries even if they also had exsanguinating hemorrhage. Furthermore, at Loma Linda University Medical Center we will have the opportunity to randomize patients to receive whole blood as their first transfusion, thus maximizing the potential benefits. Finally, we have the opportunity to study the coagulopathy associated with these patients by using viscoelastic testing.

b. Objectives

1. Evaluate PRBC equivalents transfused in each group in the first 24 hours (Primary outcome)
2. Evaluate total transfusion in each group in the first 24 hours (Secondary Outcome) including breakdown by FFP equivalents, platelet units, and cryoprecipitate
3. Evaluate 6 hour, 24 hour, and hospital mortality (Secondary Outcome)
4. Evaluate ICU outcomes in each group:
 1. ICU length of stay

- 2. Ventilator days
- 3. SOFA score on day of ICU discharge
- 4. Presence of ARDS?
- 5. Presence of TRALI?
- 6. Presence of DVT/PE?
- 7. Necessity for Dialysis?
- 8. Necessity for Tracheostomy?
- 5. Evaluate viscoelastic testing parameters in both groups when sent on arrival in ICU
 - 1. Percentage of patients with EXTEM clotting time > 80 sec
 - 2. Percentage of patients with EXTEM amplitude at 10 min < 40mm and FIBTEM amplitude at 10 min \leq 10mm
 - 3. Percentage of patients with EXTEM amplitude at 10 min < 40mm and FIBTEM amplitude at 10 min > 10mm
 - 4. Percentage of patients with maximum thrombolysis > 15%
- 6. Interval analyses to be performed after 6 and 12 months with provision to continue the study out to 24 months.
 - 1. Stopping rule: A statistically significant difference in hospital mortality at 6 months or 12 months
 - 1. If in favor of LTOWB, consideration of trial termination and making LTOWB the primary standard of care for all trauma patients receiving emergency transfusion except for child-bearing age females (unless Rh immunoglobulin can be administered)
 - 2. If in favor of component therapy, consideration of trial termination and making component therapy the primary standard care for all trauma patients receiving emergency transfusion
- c. Procedures involved (Research Interventions)

*Chronological order of all research interventions, **distinguishing standard of care vs. research intervention.***

- 1. Level A trauma paged out with gender of patient
- 2. For female patients, care proceeds as normal
 - 1. Standard trauma cooler containing 4 units O- PRBC and 4 units FFP dispatched to trauma bay (if overall supply is short the first cooler may contain 2 units O- PRBC and 2 units FFP)
 - 2. Transfusion proceeds per trauma and ED team
 - 3. Patient data not included in the study

3. For male patients, the blood bank will randomize patients to the LTOWB group or the CT (component therapy) group based on a prespecified calendar-based randomization scheme by week:
 1. LTOWB: Cooler containing 2 or 4 units of LTOWB dispatched to trauma bay depending on supply
 2. CT: Standard trauma cooler containing 4 units O+ PRBC and 4 units FFP dispatched to trauma bay (if overall supply is short the first cooler may contain 2 units O+ PRBC and 2 units FFP)
 3. Transfusion proceeds per trauma and ED team
 4. Blood work (CBC, BMP, tox screen, ROTEM viscoelastic test, PT/INR, PTT, venous lactate) sent as per standard of care for all patients.
 5. Hemorrhage control and other diagnostic evaluations performed in all patients per standard of care.
 6. Patients arrive in ICU and have additional blood work (CBC, CMP, possibly ABG, ROTEM viscoelastic test, PT/INR, PTT, venous lactate, possibly fibrinogen) sent per standard of care by the ICU team.
 7. Clinical data on survival and transfusion monitored
- d. Alternative procedures, if any, that are not included in the study but might be advantageous to the subject. N/A
- e. If any deception is required for validity of this study, explain why this is necessary and how subject(s) will be debriefed. N/A
- f. Concise review of literature that supports the rationale, objectives, and methodology of the proposed study.

Whole blood transfusion has been used in multiple military conflicts for more than one hundred years. (1) As mentioned above, during the 1960's and 1970's advancements in blood banking allowed for the transfusion of isolated components, although this was done without detailed investigation. The institution first of fresh whole blood, followed by cold-stored whole blood, was made necessary during the recent conflicts in Iraq and Afghanistan. Cold-stored whole blood has since been adapted for the civilian setting, with one unit considered equivalent to 1 unit of PRBC and 1 unit of FFP.

Low-titer O negative whole blood has been safely administered through a trial performed at UT Houston, with no transfusion reactions in the whole blood group. (1) The group at Barnes-Jewish Hospital in St. Louis, MO, performed a prospective observational trial over an eighteen-month comparing outcomes before and after whole blood was introduced into their system. In this study of 86 patients, there was no unadjusted difference in survival, although there was an improved odds of survival in the whole blood group after adjusting for maximum clot firmness as measured by viscoelastic testing. (2) A retrospective cohort study of 270 matched patients indicated no difference in clinical outcomes. (3) A large retrospective analysis of the data from the Trauma Quality Improvement Program indicated that 280 patients receiving whole blood had reduced 24-hour and hospital mortality, reduced rate of complications after adjustment for clinical covariates. (4) However, none of these studies are randomized, most use O-negative whole blood or a mixture of O-positive and O-negative whole blood, and there is no discussion of alloimmunization of female recipients against the Rh positive whole blood.

There is only one previously published randomized clinical trial of leukoreduced type specific whole blood for type O and type A recipients. In this trial of 107 patients, performed at the

University of Texas at Houston, patients were blood typed prior to inclusion in the study. Furthermore, all type B and AB patients were excluded, as were patients with significant traumatic brain injury or if they received more than 4 units of blood prior to randomization. Patients were also excluded if they could not, in the judgment of the attending surgeon, wait for blood typing. Thus, out of 357 patients who could have met criteria for inclusion, only 107 were actually randomized, introducing selection bias. In particular, the exclusion for the patients felt to be “too sick to wait” for blood typing may have excluded some sicker patients who would have benefited from whole blood. However, this study did demonstrate a reduction in transfusion volumes for patients after those with brain injury were excluded. (5)

As can be seen, the current field of literature leaves multiple unanswered questions that will be answered by the proposed study.

- 1) Does transfusion with low-titer O-positive whole blood reduce the amount of transfusion within 24 hours of arrival?
- 2) Does transfusion with low-titer O-positive whole blood reduce 6 hour, 24 hour, or hospital mortality?
- 3) What is the effect of low-titer O-positive whole blood transfusion on coagulopathy after trauma, as demonstrated by viscoelastic testing?
- 4) Is the potential benefit of transfusion with low-titer O-positive whole blood restricted only to patients receiving massive transfusion (6 units PRBC or more) or in all patients receiving emergency transfusion?
 - g. If an Investigational New Drug (IND) is involved, provide the following information: (1) name of drug, (2) source of drug, (3) dosage and schedule of administration, (4) status with Food and Drug Administration and IND#, (5) review of animal studies and previous human studies, (6) reported side effects

N/A

- h. For an approved drug used in an experiment, provide similar information: (1) name, (2) source, (3) dosage, (4) how administered, (5) side effects.

N/A

- i. If an Investigational Device (ID) is involved, provide the following information: (1) name of device, (2) manufacturer, (3) status with Food and Drug Administration and ID#, (4) review of animal studies and previous human studies, (5) reported adverse effects.

N/A

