11. DATA ANALYSIS

Analysis to be performed by median/IQR with nonparametric comparison of medians for central tendency. P value of 0.05 indicates statistical significance. Patients with death on arrival will be excluded from data reporting as they are a different patient population. Intentional sub-analysis will be performed on patients who received less than 6 units PRBC or equivalent in the first 4 hours or 6 units and more PRBC in the first 4 hours (massive transfusion). Also, an intentional sub-analysis will be performed on the patients who were classified as dead on arrival. Separate sub-analyses will be performed on patients with Abbreviated Injury Score (Head) of 3 or greater indicating severe traumatic brain injury.

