13. BENEFIT(S)

It is possible that patients transfused with LTO+WB may experience improved resolution of coagulopathy. As such it is possible that they may experience either reduced transfusion or even a survival benefit. Thus far, available literature has not demonstrated a survival benefit consistently, nor has it consistently demonstrated reduced need for transfusion. As such, it is felt by the investigators that clinical equipoise still exists between the two randomized treatment arms.

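### Patients who die after arrival but within 24 hours enter the primary transfusion comparison with counts cut off at death, and nothing planned separates earlier death from lower need

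*Combined protocol and SAP*

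**What the plan says.** All references are to the combined protocol and SAP.

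- Section 8.b, item 1 sets the primary outcome: "Evaluate PRBC equivalents transfused in each group in the first 24 hours (Primary outcome". Section 8.f puts the matching question first: "Does transfusion with low-titer O-positive whole blood reduce the amount of transfusion within 24 hours of arrival".
- Section 11 gives the method: "Analysis to be performed by median/IQR with nonparametric comparison of medians for central tendency". No test is named.
- Section 11 removes one group of deaths: "Patients with death on arrival will be excluded from data reporting as they are a different patient population". Section 5 gives the reason, describing these as patients "who will have their data excluded to eliminate the effect of survivor bias in the remaining subjects".
- Section 8.b, item 3 makes mortality a separate outcome: "Evaluate 6 hour, 24 hour, and hospital mortality (Secondary Outcome".
- Section 11 plans sub-analyses by units in the first 4 hours (below 6, or 6 and more), of dead-on-arrival patients, and of patients with a head injury score of 3 or greater.

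No section says how a patient who dies after arrival but before 24 hours is counted. None links the transfusion result to survival. Section 9 collects units by location, death in the emergency department and in the hemorrhage control environment, and yes/no flags for death by 6 and by 24 hours. It lists no time of death.

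**The concern.** A patient who dies soon after arrival stops receiving blood. In a raw 24-hour count, that patient can look like one who needed little. The plan recognises survivor bias as a reason to set dead-on-arrival patients aside, but has no rule for deaths shortly afterwards, where a similar problem arises.

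If the arms have the same 24-hour mortality, this mostly adds noise. If they differ, the arm with more deaths looks better when deaths follow few units and worse when they follow many. The plan regards a difference as possible. Section 8.f cites a retrospective analysis in which "280 patients receiving whole blood had reduced 24-hour and hospital mortality", and section 13 says of LTOWB patients: "As such it is possible that they may experience either reduced transfusion or even a survival benefit".

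The answer to the first study question is at stake. If LTOWB keeps alive patients who would have died after few units, a real saving can be missed, or LTOWB can appear to use more blood. If early deaths follow heavy transfusion, fewer deaths can pass for lower need. The planned sub-analyses do not resolve this. The 4-hour split, for example, puts an early death after few units in the low-transfusion group.

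**Working it through.** **The plan's own figure.** Section 6 gives a 2-unit difference (6 versus 4), SD about 4, alpha 0.05 and power 90%. Per arm, n = 2(1.960 + 1.282)² × 4² / 2² = 84.1, so 85 per arm and 170 in total. The plan states 190 and projects 200. The stated size is conservative on its own inputs (power about 94% at 100 per arm), and the point below does not depend on it.

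**Inputs to the check.** From section 6: 100 per arm (200 in total, with 1:1 assumed because no ratio is given), median 6, SD about 4. Survivor counts are lognormal with sigma 0.646, rounded, minimum 1. The quartiles are then 6 × exp(±0.6745 × 0.646), that is 3.88 and 9.28, and 5.40 / 1.35 = 4.0 matches the SD taken from the interquartile range. Assumed: 24-hour mortality, units at death, a two-sided Wilcoxon rank-sum test at 0.05, and that the median of 6 applies to survivors. Section 6 gives that median for the whole component group.

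**If LTOWB lowers mortality** (mortality written CT/LTOWB; nominal error 2.5% per side):

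| Units received by those who die | False 'LTOWB higher', 20/10% | False 'LTOWB higher', 30/15% | Power for a true 6-to-4 reduction, 20/10% |
|---|---|---|---|
| all at 1-4 | 15% | 29% | 76% |
| 10-60% of own need | 13% | 26% | 81% |
| half at 1-4, half at 4-16 | 4.5% | 5.7% | 93% |
| spread over 1-12 | about 2.5% | about 2.5% | 97% |
| all at 4-16 | 0.6% | 0.4% | 99% |

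The false-positive columns assume no effect on need. At equal 20% mortality, power is about 90-93%. With all deaths at 4-16 units the error moves to the other side: false 'LTOWB lower' is 7.4% at 20/10% and 11.8% at 30/15%.

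**If LTOWB raises mortality**, with no effect on need and all deaths at 1-4 units, false 'LTOWB lower' is 6.6% at 20/25%, 15.9% at 10/20%, 29.3% at 15/30% and 47.1% at 20/40%. With deaths at 2-10 units it stays at about 3% even when mortality doubles.

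**How much the planned mortality comparison would flag.** Of the false 'lower' results with deaths at 1-4 units, the share that also shows a significant 24-hour mortality difference (unadjusted two-sided z-test, 0.05) is 52.7%, 79.4%, 93.2% and 97.9% in the same four settings. The unflagged remainder, as a share of all trials, is:

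- 20/25%: 6.6 × (1 − 0.527) = 3.1%
- 10/20%: 15.9 × (1 − 0.794) = 3.3%
- 15/30%: 29.3 × (1 − 0.932) = 2.0%
- 20/40%: 47.1 × (1 − 0.979) = 1.0%

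On the other side, unflagged false 'higher' with deaths at 1-4 units is 3.2% at 20/10% and 2.2% at 30/15%.

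**A second model.** Negative binomial counts, with death more likely at higher need and those who die receiving 10-60% of what they would have needed, give the same direction. With identical need, false 'lower' is 24% at 15/25% and 44% at 15/30%. Power for a true 2-unit saving is 92% at equal 15% mortality, 64% at 25/15% and 45% at 30/15%.

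**What a worst-rank analysis does.** Tying all 24-hour deaths at the worst rank gives about 76-77% power for a true 6-to-4 reduction at equal 20% mortality. With no effect on need it favours LTOWB in about 23% of trials at 20/10% and 45% at 30/15%. It therefore mixes mortality with need and cannot separate them.

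**The case against.** The strongest objection is that the large figures come from the edges. They need nearly every early death to follow few units, or every one to follow many. A trial that takes in both exsanguinating patients and severe brain injuries may well have a mixture, and then the distortion nearly cancels. This stands, and it limits the weight of the point.

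Second, 24-hour mortality by arm is already a secondary outcome, so a reader would see a wide imbalance. This largely stands: false results without a significant mortality difference are about as frequent as the nominal 2.5%. But a separate mortality comparison does not show whether fewer units meant less need or earlier death.

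Third, units actually transfused by 24 hours or death is a legitimate outcome and fits the question as worded. This stands, and is why the raw count should remain primary.

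Two stronger readings are tempting. A reader might infer that a harmful LTOWB arm could readily pass as blood-sparing. The documents do not support that: it takes a marked excess of deaths with few units before them, and the planned mortality comparison would usually show it. A reader might also infer that the plan expects a wide mortality gap. Section 8.f also reports a study of 86 patients with no unadjusted survival difference and a matched study of 270 with no difference in clinical outcomes. Section 13 says a survival benefit has not been shown consistently.

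**Conclusion.** The point holds as a cheap improvement. As written, post-arrival deaths within 24 hours enter the primary comparison with truncated counts, and no planned analysis separates earlier death from lower need.

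How much this matters cannot be fixed from the documents. It depends on the mortality gap and on how many units those who die have received, and both are assumed here. At mortality of 20/10% to 30/15%, error on one side ranges from about nominal to about 30%. Power for a true 6-to-4 reduction at 20/10% ranges from about 76% to 99%. The distortion is material only when the gap is wide and deaths cluster at few or at many units. The documents do not show that the primary outcome is invalid or that it should be replaced.

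**What to change.** Keep the raw count as primary and add to section 11:

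> PRBC equivalents are counted to 24 hours or death. PRBC equivalents are also reported by arm separately for patients alive and dead at 24 hours (after the dead-on-arrival exclusion), beside 24-hour mortality by arm, and the primary result is interpreted together with these. As a supportive analysis, the same rank test is repeated with deaths within 24 hours tied at the worst rank; it reflects mortality as well as transfusion need and is not a condition for claiming reduced transfusion.

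The cost is one table and one extra analysis. The 24-hour death flag and the units by location are already on the section 9 data list. The primary test, its alpha and its power do not change.

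The table must be read as descriptive, because survival is a post-randomisation outcome. The worst-rank test is weaker at equal mortality and ranks a non-hemorrhagic death worst whatever its transfusion need. It also fails to flag a false 'lower' when LTOWB lowers mortality and deaths follow 4-16 units: at 20/10%, 97% of those results are significant in it too. In that case the units given before death, by arm, are what inform the reader, so the table should lead.

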
Lactate

LLUMC HCE ABG results #2 (last in HCE)

pH

Hgb

Lactate

LLUMC HCE ROTEM results #1 (first in HCE, if sent)

EXTEM CT

EXTEM A10

If EXTEM A10 < 40mm, FIBTEM A10

EXTEM ML

LLUMC HCE ROTEM results #2 (last in HCE, if sent)

EXTEM CT

EXTEM A10

If EXTEM A10 < 40mm, FIBTEM A10

EXTEM ML

LLUMC ICU/Floor Transfusion within first 24 hours (not including blood given prior to LLUMC, in LLUMC ED, and in LLUMC HCE)

LLUMC ICU WB (# units)

LLUMC ICU PRBC (# units)

LLUMC ICU FFP (# units)

LLUMC ICU PLT (# unitss

LLUMC ICU Cryo (# units)

LLUMC ICU Crystalloid (# liters)

LLUMC ICU ABG results

pH

Hgb

Lactate

LLUMC ICU Hgb from CBC

LLUMC ICU PLT count from CBC

LLUMC ICU INR

LLUMC ICU PTT

LLUMC ICU Fibrinogen

LLUMC ICU ROTEM results

EXTEM CT

EXTEM A10

If EXTEM A10 < 40mm, FIBTEM A10

EXTEM ML

Clinical Endpoints

Patient Dead on Arrival (0=no, 1=yes)

Patient Died within 6 hours of arrival (0=no, 1=yes)

Patient Died within 24 hours of arrival (0=no, 1=yes)

Patient Died Prior to Discharge (0=no, 1=yes)

Duration of Mechanical Ventilation (Days)

Duration of ICU Stay (Days)

Duration of Hospital Stay (Days)

Presence of ARDS?

Presence of TRALI?

Presence of DVT/PE?

SOFA Score on Day of ICU Discharge

Need for Dialysis During Hospitalization (0=no, 1=yes)

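### No rule says how deaths after arrival enter ICU stay, ventilator days or SOFA at ICU discharge, so the durations can favour the arm with more early deaths

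*Combined protocol and SAP*

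**What the plan says.** All references are to the combined protocol and SAP.

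- **Section 8b, item 4 (ICU outcomes)** lists "ICU length of stay", "Ventilator days" and "SOFA score on day of ICU discharge". No denominator is given, and no value is assigned to a patient who dies.
- **Section 9, Clinical Endpoints,** holds ICU stay and mechanical ventilation as total days, and "SOFA Score on Day of ICU Discharge" with no code for death. It also has yes/no fields for death by 6 hours, by 24 hours and before hospital discharge. Earlier in the form are fields for death in the ED and in the hemorrhage control environment (HCE). No field records death in the ICU, and no date of death is listed.
- **Section 11** gives one method for all outcomes: "Analysis to be performed by median/IQR with nonparametric comparison of medians for central tendency".
- **Sections 5 and 11** contain the only death-related rule. Patients dead on arrival are removed from the main data, for the stated purpose of avoiding survivor bias, and are examined in a separate sub-analysis.
- **Section 8b, item 3** makes mortality at 6 hours, 24 hours and in hospital a secondary outcome. Section 8f asks whether whole blood lowers it.

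**The concern.** A duration that ends at death is short for a bad reason. In a trial of bleeding patients, some will die within hours, before or shortly after reaching the ICU. If they are counted with the days they accrued, a death on day 1 ranks with the best results for ventilation and ICU stay. If one product prevents early deaths, the extra survivors add ICU and ventilator days to that arm, so the better arm can look worse.

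The trigger is a mortality difference between arms, which is one of the trial's own questions. The plan recognises survivor bias but deals with it only for patients dead on arrival. What is at stake is how the ICU outcomes are read, and whether the handling of deaths is settled before anyone has seen the data.

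**Working it through.** **Plan's own figure.** There is none to reproduce. The sample-size calculation in Section 6 concerns 24-hour red-cell equivalents, and no rates or durations are given for the ICU outcomes. Only the projected total of 200 is used here, taken as 100 per arm (1:1 is assumed, as the ratio is not stated).

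**Assumed inputs.** Ventilation need is the same in both arms: lognormal, median 4 days, log-SD σ = 0.8 or 1.0. Of all deaths, 70% are early and recorded as 1 day; in the approximation below, later deaths keep their full duration. Arm A has the higher mortality m. The test is Mann-Whitney, two-sided 5%, so 2.5% is nominal in each direction.

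**Approximation by hand.**

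1. Early-death share: e = 0.7 × m.
2. Chance that a non-early-death patient needs less than 1 day: π = Φ(−ln 4 / σ), which is 0.042 at σ = 0.8 and 0.083 at σ = 1.0.
3. P(A shorter than B) + ½P(tie) = 0.5 + (e_A − e_B)(0.5 − π).
4. Null standard error: √[(2×100 + 1)/(12×100²)] = √(201/120,000) = 0.0409.
5. Chance of a significant result favouring A ≈ Φ(shift/0.0409 − 1.96).

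| Mortality A v B | e_A − e_B | Shift (σ 0.8 / 1.0) | Shift ÷ SE | Favours A, by formula | Favours A, simulated |
|---|---|---|---|---|---|
| 30% v 15% | 0.105 | 0.048 / 0.044 | 1.18 / 1.07 | 22% / 19% | 20-24% |
| 25% v 15% | 0.070 | 0.032 / 0.029 | 0.78 / 0.71 | 12% / 11% | 11-12% |
| 20% v 15% | 0.035 | 0.016 / 0.015 | 0.39 / 0.36 | 6% / 5% | about 5% |
| equal | 0 | 0 | 0 | 2.5% | about 2% |

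Formula and simulation agree. The formula shows that the signal is proportional to the gap in early death and vanishes when there is no gap.

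**Sensitivity.** If only half of deaths are early, the simulated figures fall to 13% (30% v 15%) and 9% (25% v 15%). For ICU stay under a harsher assumption (median 6 days if alive, log-SD 1, every modelled death early at 0-1 day):

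- Early death 25% v 15%: medians 3.95 v 4.84 days, and 21.5% of trials favour the arm with more deaths.
- Early death 30% v 15%: medians 3.42 v 4.85 days, and 43.9% of trials.

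**Leaving early deaths out.** The wrong-direction rate for ventilator days then returns to about 2%, but only because the simulation makes death unrelated to ventilation need. In real patients that is doubtful, and the groups compared would be selected after randomisation.

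**Scoring death as worst.** At 30% v 15% mortality, ventilator-free days significantly favour the lower-mortality arm in about 44% of trials. The direction is then right.

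**SOFA.** No arithmetic applies. The score is defined on a day that a patient who dies before ICU discharge never reaches, so it is missing because of the outcome.

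**The case against.** **The plan does not say that early deaths count as 0-1 days.** A reader might infer that it scores day-1 deaths as excellent results. The documents do not support that. These are listed as ICU outcomes, the form separately codes deaths before the ICU, and restriction to patients admitted to the ICU is equally open. This stands. The defect is that the rule is undefined, and each of the two obvious readings has a problem.

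**A real benefit would not simply be reported as harm.** Mortality is presented for the same arms. In simulation at 30% v 15%, mortality was itself significant in about 88% of the trials where ventilator days misled; at 25% v 15% the figure was about 64-67%. This stands in large part. It still leaves about 12% and about a third of misleading trials without a significant mortality difference, and the plan gives no rule for reading the two results together.

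**The ICU outcomes are not labelled secondary.** Section 8b attaches that label only to items 2 and 3. A reader might treat the ICU items as declared secondary outcomes, but the text does not say so. They play no part in the primary outcome, the sample size or the stopping rule.

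**The sizes rest on assumed rates.** True. Section 13 says that a survival benefit has not been shown consistently, and a 5-point gap produces only a small excess.

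**Free days mostly re-express mortality.** With identical ventilation need, their signal comes from the mortality difference. That is a fair limit, and the reason to tabulate the components. Competing-risk analysis is a legitimate alternative.

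**Conclusion.** The point holds as a gap in the analysis rules with a predictable direction of bias. ICU stay and ventilator days are raw durations, SOFA at ICU discharge is undefined for patients who die first, and nothing covers deaths after arrival.

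The durations mislead only if early mortality differs between arms and deaths enter with their short recorded durations. Under the inputs assumed above, the wrong-direction rate is about 20-24%, 11-12% and 5% for mortality gaps of 15, 10 and 5 points, against 2.5% nominal. These figures illustrate the mechanism. They are not estimates for this trial, because the documents supply no mortality rates or ventilation times. The consequence is confined to the interpretation of the ICU outcomes. The change should be made, but it does not threaten the trial's main conclusion.

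**What to change.** Before analysis, state the following.

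1. **Durations.** Make ventilator-free and ICU-free days to day 28 the between-arm comparison in place of raw durations, in all eligible randomised patients not dead on arrival. Score any in-hospital death 0; otherwise use 28 minus the recorded total days, with a floor of 0. The recorded totals and the field for death before hospital discharge are enough. Because the form lists no start or stop dates, days falling beyond day 28 can only be approximated, and the plan should say so.
2. **SOFA.** Assign the worst rank to a patient with an ED or HCE death, or with an in-hospital death and no ICU-discharge SOFA. This working definition is needed because no field records death in the ICU directly.
3. **Description.** Show raw ICU and ventilator days in survivors as description only, without a between-arm test.
4. **Components.** Tabulate mortality and duration by arm beside each free-days result.

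The cost is mainly analysis wording, with no new data collection if the approximation at day 28 is accepted. The downside is that free days mix death and duration, which item 4 makes visible.
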